A cost utility analysis will be performed if the results of this study show clear benefit of sodium-selenite administration compared to placebo. The cost effectiveness of sodium-selenite administration compared to placebo will be assessed in terms of the incremental cost per quality adjusted life year (QALY) gained from the perspective of health care system. Analysis will incorporate data on resource use and patients utility values up to 6 months post sodium-selenite administration given the assumption that no long term differences in outcome are expected. Resource use will be assessed by data collected at the follow up interviews. Utility values would be derived from SF-36 using the algorithm proposed by Brazier et al. QALYs will be estimated for each patient within the clinical trial using the total area under the curve method. The incremental cost and QALY will be estimated using a regression analysis approach. Uncertainty in the analysis will be addressed by estimating 95% CIs using a non-parametric bootstrapping method. Further details of the cost utility analysis, should it be indicated, will be detailed in a separate document.

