6.2.2 Secondary outcomes

Secondary binary outcomes such as cardiovascular complications, postoperative delirium, re-admissions, hospital-acquired infections and 30-day mortality will be compared between groups by a logistic mixed effects model with site included as a random effect.¹ Odds ratios with 95% confidence intervals will be reported.

Six-month mortality will be described by group using Kaplan-Meier curves. Survival will be compared by a hazard ratio with 95% confidence intervals and corresponding Wald test. Estimates will be derived from the Cox proportional hazards model with a random frailty for site. If the proportional hazards assumption is clearly and meaningfully violated, we will report a smoothed time dependent hazard ratio over time. However, the aforementioned overall Wald test will remain the primary test of statistical significance. Patients will be censored at the earliest of 183 days post randomization or last known follow-up.

Length of ICU and hospital stay will be summarized by arm using the quartiles of time to live discharge estimated from the subdistribution cumulative incidence function (CIF) where death is treated as a competing risk precluding the possibility of discharge. The between arm difference in time to live discharge will be tested using the Wald test from the Cox proportional hazards model with site as a random frailty to account for potential between site heterogeneity. Patients who die prior to discharge will be censored after the end of the follow-up period to account for the competing risk of death. This will yield virtually the same results as the Fine and Gray approach treating death as a competing risk precluding discharge, except we will have incorporated ICU as a random effect. This outcome is also known as time-to-discharge-alive (TTDA).

The SF-36, Barthel Index and frailty scale will be collected at baseline. At 30 days, 3 months and 6 months after surgery, we will repeat the Barthel Index and SF-36 and collect return to work data. The SF-36 physical and mental summary scales and the Barthel index will be treated as continuous variables and analyzed using a linear mixed effects model for longitudinal data. In order to include all patients

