6.2.4 Adjustment for covariates

Analysis involving hypothesis testing or creation of confidence intervals will control for site which was the sole stratification factor at randomization. No other covariates will be controlled for.

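### Read literally, SAP 6.2.4 leaves site as the only covariate in the QALY regression, so baseline SF-36 utility, which is collected, would go unused there

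*SAP*

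**What the plan says.** Section 6.1.5 (Cost Utility Analysis) sets out four relevant steps:

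- Utilities: "Utility values would be derived from SF-36 using the algorithm proposed by Brazier et al".
- QALYs: "QALYs will be estimated for each patient within the clinical trial using the total area under the curve method".
- Treatment contrast: "The incremental cost and QALY will be estimated using a regression analysis approach". No covariate is named, not even site.
- Uncertainty: "Uncertainty in the analysis will be addressed by estimating 95% CIs using a non-parametric bootstrapping method".

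The analysis is conditional on the trial showing a clear benefit, and the section leaves further detail to a separate document.

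Section 6.2.4 gives a general covariate rule: "Analysis involving hypothesis testing or creation of confidence intervals will control for site which was the sole stratification factor at randomization". The next sentence is "No other covariates will be controlled for". No exception is given.

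Section 6.2.2 shows that the data exist: "The SF-36, Barthel Index and frailty scale will be collected at baseline", and "At 30 days, 3 months and 6 months after surgery, we will repeat the Barthel Index and SF-36 and collect return to work data". For the SF-36 summary scales themselves, the same section uses baseline through a constrained longitudinal model, in which baseline is one of the outcomes and not a covariate.

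**The concern.** The cost utility analysis produces 95% confidence intervals, so the wording of 6.2.4 reaches it. The QALY regression would then contain arm and site only.

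Baseline utility is an obvious covariate for an area-under-the-curve QALY. It is normally the first point on the curve, and it correlates with the later utilities that make up most of the area. If it is left out, a chance difference between arms at baseline feeds into the incremental QALY, which is the denominator of the cost per QALY. Over six months that increment is likely to be small, so a modest shift can matter. The interval is also wider than the collected data require.

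Timing adds to this. Section 1.3 says the SAP is meant to record the plan before outcomes by arm are examined. The cost utility analysis is triggered only by a favourable result, and the SAP gives no date for the separate document. If baseline utility were first added there, it might be a covariate choice made with results known, and it would depart from the literal text of 6.2.4.

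**Working it through.** The SAP states no utility SD, correlation, QALY difference or power for this analysis, so there is no figure to reproduce. The check is the reading of 6.1.5 against 6.2.4 above, plus an illustration of size.

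**Inputs from the SAP.** SF-36 at baseline, 30 days, 3 months and 6 months (6.2.2); 700 per arm and 4% 30-day mortality (4.3).

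**Assumptions.** Visits at days 0, 30, 91 and 182; trapezoid rule starting at baseline (6.1.5 does not state the start point); utility SD σ = 0.15 at each visit; equal correlation ρ = 0.3, 0.5 or 0.7 between visits; mean utility μ = 0.6 to 0.7; complete utility data in survivors; deaths before day 30, unrelated to baseline utility, with utility 0 at all later visits.

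**Step 1: weights.** The trapezoid weights are 15, 45.5, 76 and 45.5 days. Divided by 365.25 they are 0.0411, 0.1246, 0.2081 and 0.1246 years. The three follow-up weights sum to W = 0.4572. Baseline itself is 15/182 = 8.2% of the area, so most of the effect comes through its correlation with later utility.

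**Step 2: chance imbalance.** The SE of the baseline difference is 0.15 × √(2/700) = 0.0080, and 1.96 SE is 0.0157.

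**Step 3: no deaths.** The slope of QALY on baseline utility is b = 0.0411 + ρ × 0.4572, which is 0.178, 0.270 and 0.361. The expected shift is 0.0157 × b. With R² the squared correlation of QALY and baseline utility, adjustment leaves a fraction 1 − R² of the variance and √(1 − R²) of the interval width.

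**Step 4: 4% deaths.** Write Q = w₀u₀ + A·F, where w₀ and u₀ are the baseline weight and utility, F is the follow-up area and A = 1 for survivors. Then b = w₀ + 0.96ρW, and

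Var(Q) = w₀²σ² + 2w₀(0.96)Cov(u₀,F) + 0.96 Var(F) + 0.04 × 0.96 × (μW)².

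Example with ρ = 0.5 and μ = 0.65:

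- Var(Q) = 0.00004 + 0.00041 + 0.00306 + 0.00339 = 0.0069
- b = 0.0411 + 0.96 × 0.5 × 0.4572 = 0.2605
- R² = 0.2605² × 0.0225 / 0.0069 = 0.22
- SE of the incremental QALY = √(2 × 0.0069/700) = 0.0044
- Shift = 0.0157 × 0.2605 = 0.0041, or 0.92 SE
- The interval narrows by 1 − √(1 − 0.22) = 12%

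**Results** (ranges with deaths run over μ = 0.6 to 0.7):

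| ρ | Deaths | Shift (QALY) | Shift / SE | Variance removed | CI narrower by |
|---|---|---|---|---|---|
| 0.3 | none | 0.0028 | 0.98 | 25% | 13% |
| 0.5 | none | 0.0042 | 1.31 | 45% | 26% |
| 0.7 | none | 0.0057 | 1.60 | 66% | 42% |
| 0.3 | 4% | 0.0027 | 0.62–0.68 | 10–12% | 5–6% |
| 0.5 | 4% | 0.0041 | 0.89–0.96 | 21–24% | 11–13% |
| 0.7 | 4% | 0.0055 | 1.13–1.21 | 33–38% | 18–21% |

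Deaths add QALY variance that baseline utility does not explain. They roughly halve the gain in precision but leave the shift almost unchanged. The rows with deaths are the relevant ones, because they use the SAP's own mortality figure.

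**The case against.** The strongest reply is that the SAP does not fix the QALY model at all. Section 6.1.5 names no covariates and refers to a separate document, which could specify baseline utility. Section 6.2.4 also sits among the methods for the primary, secondary and additional outcomes, while the cost utility analysis sits in 6.1.5, so a dedicated economic plan might be expected to govern its own model. This has weight. A reader might infer that QALYs will definitely be estimated without baseline utility, and the SAP does not say that. What survives is that 6.2.4 is worded by type of output, not by section, and contains no exception. The separate document could add the covariate only by departing from that wording.

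A reader might also infer that the SAP rejects any use of baseline quality of life. It does not: the constrained longitudinal model in 6.2.2 uses baseline SF-36. The literal exclusion is of covariates other than site.

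Nor does the plan give a biased estimate. Randomisation keeps the unadjusted difference unbiased on average, and an imbalance of 1.96 SE or more in either direction is about a 1-in-20 event. The cost is precision and exposure to chance imbalance.

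Finally, the analysis is conditional and bears on no primary, secondary or safety conclusion. That is true, and it limits the importance of the point.

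**Conclusion.** The point holds as a minor one: two sections need reconciling, and a useful covariate is excluded by a rule probably written with other analyses in mind. With 4% early deaths, a 1.96-SE baseline imbalance would move the incremental QALY by roughly 0.6 to 1.2 of its standard errors, and adjustment would remove about 10 to 38% of the variance.

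The much larger gains in the no-death rows should not be quoted for this trial. The utility SD, mean and correlations are assumptions. The 4% covers 30 days only; further deaths up to 6 months, unrelated to baseline utility, would reduce the gain again. The conclusion that baseline utility should be allowed into the model does not depend on the exact values, only on its correlating with later utility.

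**What to change.** Add to 6.1.5: *The QALY regression will include baseline SF-36-derived utility and site as covariates, and the adjusted model will be refitted in each bootstrap sample.* Add to 6.2.4 that the QALY regression in 6.1.5 is an exception to the site-only rule. The separate cost utility document keeps the remaining details, including the visits and start point of the area under the curve.

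The cost is two sentences and one covariate from data already collected. The one downside is that patients without a baseline SF-36 need that covariate imputed, by mean or multiple imputation, and the method should be named. Section 1.1 records that no outcome results by arm existed when version 1 was finalised. A dated revision made while that is still so would keep the choice prespecified; a later one should be labelled as such.

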6.2 Analysis Methods

6.2.1 Primary outcome

To test the between arm difference of PODS free days (PFDs) we will use the van Elteren test which is a stratified version of the Wilcoxon rank-sum test where the ranking is done within site to control for heterogeneity in PFDs between sites. This is a slight deviation from the original protocol which planned to use the un-stratified Wilcoxon rank-sum test. The daily proportion of patients alive and free of life sustaining therapy by arm over the first 30 days will be reported in a table or graphically. In this table or figure we will also report the daily usage rates of each specific life sustaining therapy. The key summary measure for the effect size of PFDs will be a within site concordance index (c-index). The within site c-index estimates the probability that a patient in the intervention arm will have more PFDs than a patient in the control arm from the same site. The within site c-index can range from 0 to 1, where 1 indicates that within each site every patient in the intervention arm has more PFDs than any patient in the control arm, 0 is the converse, and 0.5 would indicate no difference between arms. The within site c-index will be defined as follows: 1) within each site, compare every patient in the intervention arm to every patient in the control arm, so for example if a site had 10 patient in the intervention arm and 12 patents in the control arm there would be 120 comparisons, 2) assign each comparison a value if 1 the intervention arm patient has more PFDs, 0 if the control arm patient has more PFDs and 0.5 if both arms have the same PFDs; 3) calculate the average of within site c-indexes weighting each site proportionally to the square root of the number of comparisons within the site. We will then obtain the 2.5th and 97.5th percentile of 10, 000 bootstrap samples to estimate the 95% confidence intervals of the within site c-index.

6.2.2 Secondary outcomes

Secondary binary outcomes such as cardiovascular complications, postoperative delirium, re-admissions, hospital-acquired infections and 30-day mortality will be compared between groups by a logistic mixed effects model with site included as a random effect.¹ Odds ratios with 95% confidence intervals will be reported.

Six-month mortality will be described by group using Kaplan-Meier curves. Survival will be compared by a hazard ratio with 95% confidence intervals and corresponding Wald test. Estimates will be derived from the Cox proportional hazards model with a random frailty for site. If the proportional hazards assumption is clearly and meaningfully violated, we will report a smoothed time dependent hazard ratio over time. However, the aforementioned overall Wald test will remain the primary test of statistical significance. Patients will be censored at the earliest of 183 days post randomization or last known follow-up.

Length of ICU and hospital stay will be summarized by arm using the quartiles of time to live discharge estimated from the subdistribution cumulative incidence function (CIF) where death is treated as a competing risk precluding the possibility of discharge. The between arm difference in time to live discharge will be tested using the Wald test from the Cox proportional hazards model with site as a random frailty to account for potential between site heterogeneity. Patients who die prior to discharge will be censored after the end of the follow-up period to account for the competing risk of death. This will yield virtually the same results as the Fine and Gray approach treating death as a competing risk precluding discharge, except we will have incorporated ICU as a random effect. This outcome is also known as time-to-discharge-alive (TTDA).

The SF-36, Barthel Index and frailty scale will be collected at baseline. At 30 days, 3 months and 6 months after surgery, we will repeat the Barthel Index and SF-36 and collect return to work data. The SF-36 physical and mental summary scales and the Barthel index will be treated as continuous variables and analyzed using a linear mixed effects model for longitudinal data. In order to include all patients

with a baseline assessment regardless of follow-up, we will use constrained longitudinal data analysis where the independent dummy variable indicating treatment arm (1-treatment or 0-control) will be set so to 0 at baseline for both arms but 1 post baseline for the intervention arm.^{2,3} This model will include site as a random effect and will allow for unstructured within patient correlation as estimated by restricted maximum likelihood. The focus of these secondary analyses will be primarily descriptive as these outcomes are limited to survivors and no imputation for decedents is planned. Thus, these outcomes will not be informative of treatment efficacy if they are in the opposite direction from survival. The between group difference in the change from baseline to the various follow-up time points will be described as expected means with 95% confidence intervals.

6.2.3 Additional outcomes:

Days alive and home in 6 months will be analyzed using the same approach as PFDs.

Variables collected but not specifically listed above will be described by arm at each time they were collected using counts and percentages for categorical variables and medians and quartiles or means and standard deviations for continuous variables. Post baseline differences in these variables will be tested using the Cochran-Mantel-Haenszel test stratified by site for the categorical variables and the van Elteren test stratified by site for continuous variables. Analysis of these variables will be considered exploratory so no adjustment for multiplicity will be applied to p-values, but multiplicity of tests will be considered in when interpreting these results.

Study reporting will be in accordance with the CONSORT statement.⁴

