4.1 Trial Design

A randomized, placebo-controlled, double-blind, multicentre definitive trial of 1400 patients across 20 sites in Germany and Canada, which will include the pilot study patients. An industry partner (Biosyn) will provide the product and some additional support for the European sites. Patients will be randomized to receive either a daily perioperative high-dose selenium or placebo until postoperative day 10 (maximum) or upon earlier discharge from ICU.

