4.2 Randomization

Randomization description copied from published protocol.

At each participating center the local coordinating investigator will screen daily all cardiac surgical patients scheduled to undergo cardiac surgery in the near future or on the next day. A screening

log will be kept at each site to determine the number of patients meeting the inclusion criteria, those truly eligible patients, those who consent and are randomized and reasons why potentially eligible patients did not get enrolled. Following a full explanation of the nature and purpose of the study, a written informed consent will be obtained from the patients participating in the study. At the time of enrolment into the study, patients will be randomized to receive either selenium or a matching placebo similar in appearance, consistency, volume, and smell so as to blind patients, investigators and health care practitioners as to the nature of the study medication. Patients will be consecutively randomized by a web-based randomization system (concealed and blinded) developed by the Clinical Evaluation Research Unit at the Kingston Health Sciences Centre and randomization will be stratified according to centre. Randomization will be based on the method of permuted blocks of undisclosed random size stratified by centre.

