6.2.5 Assumption checking

The analysis of the primary outcome is non-parametric so no assumptions will be checked. The proportional hazards assumption of 6-month survival will be assessed graphically.

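### Time to live discharge: a proportional site frailty combined with keeping decedents in every risk set can understate the standard error and lose power if sites differ materially in discharge speed; stratifying by site avoids both

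*SAP*

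**What the plan says.** SAP section 6.2.2 sets two rules for one Cox model of ICU and hospital stay. Site enters as a frailty, with the arm difference "tested using the Wald test from the Cox proportional hazards model with site as a random frailty to account for potential between site heterogeneity". Decedents stay at risk for discharge throughout: "Patients who die prior to discharge will be censored after the end of the follow-up period to account for the competing risk of death". The section then claims "This will yield virtually the same results as the Fine and Gray approach treating death as a competing risk precluding discharge", apart from the added random effect. It calls the grouping site in one sentence and ICU in another.

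No robust variance, site stratification or check is planned for this model. Section 6.2.5 limits its check of proportional hazards to one outcome: "The proportional hazards assumption of 6-month survival will be assessed graphically".

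Elsewhere site is handled by stratification. For the primary test, "the ranking is done within site to control for heterogeneity in PFDs between sites" (6.2.1), and the exploratory tests in 6.2.3 are also stratified by site. Section 6.2.4 requires tests and intervals to "control for site which was the sole stratification factor at randomization". Time to discharge alive is also one of the outcomes in the subgroup forest plots (6.2.6).

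**The concern.** A site frailty assumes that each site's hazard is a constant multiple of one common hazard. Because decedents remain at risk, the hazard being modelled is the subdistribution hazard. Two sites with the same mortality but different discharge speed end at the same plateau of live discharges, and proportional subdistribution hazards cannot produce that.

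Late in follow-up, the patients still at risk in a fast site are mostly decedents who can never be discharged. The frailty nevertheless gives them that site's high weight. Chance arm imbalance among these few patients then moves the score, and the model-based standard error does not allow for it. At stake are the p-values and effect estimates of two named secondary outcomes in a trial where the SAP itself anticipates differences between sites.

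**Working it through.** **Plan's own figure.** The SAP gives no error rate or power for the stay analyses. Its 90% (4.3) is for the Wilcoxon test of the primary outcome and is not at issue here.

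**Inputs from the SAP.** Size: "multicentre definitive trial of 1400 patients across 20 sites in Germany and Canada" (4.1). Allocation: "Randomization will be based on the method of permuted blocks of undisclosed random size stratified by centre" (4.2). Two-sided 5% (5.1). 30-day mortality of 4% (4.3), used as a proxy for death before discharge. A rate ratio of 1.2, borrowed from the liberation rate in 4.3.

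**Assumed.** The stay distributions and the between-site spread.

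**Step 1: what proportionality would require.** With log frailty *u*, a site's final share never discharged alive is 0.04^exp(*u*). For *u* = −0.5, 0 and +0.5 this is 14%, 4% and 0.5%. Proportionality therefore ties site mortality to discharge speed.

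Now let both sites have 4% deaths and let survivors be discharged at exactly proportional rates, ratio exp(0.5) = 1.65. A site's subdistribution hazard is its discharge rate times the share of its risk set that can still be discharged, 0.96*S*/(0.04 + 0.96*S*), where *S* is the share of survivors still in hospital.

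| *S*, reference site | *S*, fast site (*S*^1.65) | Dischargeable share, reference | Dischargeable share, fast | Ratio of subdistribution hazards |
|---|---|---|---|---|
| 1 | 1 | 0.960 | 0.960 | 1.65 |
| 0.20 | 0.070 | 0.828 | 0.628 | 1.65 × 0.628/0.828 = 1.25 |
| 0.05 | 0.0072 | 0.545 | 0.147 | 1.65 × 0.147/0.545 = 0.44 |

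The ratio falls and crosses 1, whereas a frailty holds it constant.

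**Step 2: type I error, hospital stay.** Log-normal stays, within-site log SD 0.5, 20 sites, 4% deaths, Gaussian site frailty, model-based Wald test. Three sets of runs:

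| Site log-median SD | Frailty, 4000 runs | Frailty, 2000 runs | Frailty, 1200 runs | Stratified by site |
|---|---|---|---|---|
| 0.15 | 4.9% | 5.3% | 5.0% | 4.8–5.1% |
| 0.25 | 6.4% | 6.7% | 6.2% | 4.5–5.1% |
| 0.40 | 10.0% | 9.6% | about 9% | 4.7–5.3% |

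The Monte Carlo SE near 5%, √(0.05 × 0.95/runs), is about 0.3, 0.5 and 0.6 points for the three sets. In the 2000-run set the true SD of the estimate was 0.056, 0.058 and 0.065, against a model SE of 0.055.

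**Step 3: second set-up.** Weibull stays (shape 1.5), with survivors' discharge rates exactly proportional across sites; 5000 null runs and 2000 runs at ratio 1.2 per row; 4% deaths.

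| SD of site log rate | Type I, planned | True SD / model SE | Power, planned | Power, no site term | Log ratio, planned |
|---|---|---|---|---|---|
| 0 | 4.7% | 0.0541 / 0.0546 | 68.5% | 68.4% | 0.134 |
| 0.25 | 4.9% | 0.0547 / 0.0548 | 66.4% | 64.8% | 0.132 |
| 0.50 | 6.0% | 0.0572 / 0.0549 | 61.1% | 57.3% | 0.125 |
| 0.75 | 7.9% | 0.0612 / 0.0549 | 56.1% | 46.9% | 0.117 |
| 1.00 | 10.5% | 0.0662 / 0.0550 | 51.0% | 38.0% | 0.108 |

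Stratified by site, every row gives type I error 4.8%, power 71.1% and log ratio 0.140. The results are identical because speeding up a whole site does not change ranks within it. Neither model returns log 1.2 = 0.182, since decedents dilute both; the attenuation meant here is relative to the stratified model.

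The short standard error explains the inflation. At SD 1.0, 1.96 × 0.0550/0.0662 = 1.63, and P(|Z| > 1.63) = 10.3%, against 10.5% observed. At SD 0.5, 1.96 × 0.0549/0.0572 = 1.88, which gives 6.0%, as observed.

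The two scales agree. Matching the spread of log stay times, a log-normal SD of 0.5 corresponds to a factor of (π/√6)/0.5 = 2.57, so log-median SDs of 0.15, 0.25 and 0.40 are about 0.38, 0.64 and 1.03 on the log-rate scale.

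In the log-normal set-up at SD 0.25, power was 61.5% (frailty) against 67.4% (stratified).

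**Step 4: isolating the cause.** A frailty with deaths censored at death holds 4.6–4.8%, but targets a different effect. Decedents kept plus site strata holds about 5%. Only the planned combination inflates the error.

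**The case against.** The strongest reply is that nothing shows the problem occurs in this trial. The SAP gives no between-site spread, and at a log-rate SD of 0.25 or a log-median SD of 0.15 there is no material inflation. A reader might infer that the planned test always rejects above 5%; the documents do not support that. One other set of runs gave 7.0% and 7.9% at the two smaller spreads, but its stratified comparator also ran high (6.1–6.3%), so I give it no weight.

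Further points that stand:

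- **ICU stay is less affected.** With an assumed within-site log SD of 0.9, the frailty test rejects 4.5%, 5.1% and 6.5% at site SDs of 0.15, 0.25 and 0.40.
- **The planned model is better than ignoring site.** At log-rate SD 0.5, power is 61.1% against 57.3%. The loss is relative to stratification only.
- **If sites really were proportional on the subdistribution scale, the plan would be sound:** 5.2% type I error and 89% power either way. That needs the link between mortality and speed shown in step 1, which nothing in the SAP suggests.
- **The plan does not contradict itself on site.** A reader might infer that the frailty breaches 6.2.4. It does not: a frailty controls for site, and the other model-based secondary analyses also use a random site effect.
- **The stakes are secondary.** Section 5.1 names one primary test and says secondary outcomes will be read with multiplicity in mind.

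What does not stand is that this makes the choice harmless. The SAP adds the frailty precisely because it expects site differences, and large differences are where it fails.

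**Conclusion.** The concern holds conditionally. The two rules in 6.2.2 fit together poorly when sites differ in discharge speed but have similar mortality. For hospital stay, type I error is about 5% at small site spread, 6–7% at moderate and 9–10% at large, against about 5% when stratified.

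The power loss appears earlier. At a rate ratio of 1.2 it is a few points at small spread (71.1 − 66.4 = 4.7) and about 6–10 at moderate spread (67.4 − 61.5 = 5.9; 71.1 − 61.1 = 10.0). At the largest spread examined it is 71.1 − 51.0 = 20.1.

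These sizes rest on assumed stay distributions and site spreads, on 4% as the share dying before discharge, and on a rate ratio borrowed from another endpoint. With mortality varying by site, type I error was 5.5% (log-rate SD 0.5, 5% deaths) and 8.1% (SD 1, 9% deaths). At 8% deaths, only spreads of 0 and 0.25 were examined, with no inflation. Subgroup use was not tested. The primary analysis is not affected.

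**What to change.** In SAP 6.2.2, for ICU and hospital time to live discharge, replace the site frailty with a Cox model stratified by site (a separate baseline hazard per site), keep the present handling of decedents, and report the hazard ratio with 95% CI. Keep the frailty for 6-month survival, where each site has few deaths. Name site, not ICU, as the grouping.

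The cost is one sentence and one program line (a STRATA statement in place of RANDOM). Very small sites contribute slightly less. With about 96% of patients having the event, no power loss appeared even with no site differences (71.1% against 68.5%). In the subgroup forest plots, small site-by-subgroup strata may lose some information, so stratification there is optional.
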